13.2. Planned Statistical Analysis

The primary endpoint will be an improvement in peripheral vision of at least 15 degrees in the affected visual field as measured by automated Humphrey perimetry at 6 months. The primary outcome will be compared between the treatment groups using an upper-tailed two-sample *t* test with $\alpha = 0.05$. Secondary outcome measures will include degree of cortical reorganization as assessed by fMRI, RNFL thickness as assessed by OCT, the functional vision score as assessed by the Guide for the Evaluation of Visual Impairment,

performance on neuropsychological testing, and scores on the mRS, PHQ-9, and VFQ-25.

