2.2. Rationale for Study Design

Given the growing evidence that SSRIs may improve motor recovery in stroke survivors, we hypothesize that fluoxetine will also enhance post-stroke functional recovery in the visual system. We further hypothesize that this effect will be mediated through a mechanism independent of the antidepressant and activating effects of fluoxetine. In order to investigate these hypotheses, we have designed a clinical trial in which acute ischemic stroke patients with visual field deficits will be randomized in a 1:1 ratio to fluoxetine *vs.* placebo. The degree of improvement in visual function will then be directly compared between the treatment group and the control group. Because visual recovery after stroke usually plateaus in the first 6 months, we have chosen to treat study subjects for 90 days with fluoxetine *vs.* placebo to determine if exposure to SSRIs during the peak time of recovery improves the rate or degree of recovery. This is also the duration of treatment that was used in the FLAME trial (8).

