8.3. Subject Enrollment and Randomization

Subjects will be randomized in a ratio of 1:1 to fluoxetine vs. placebo by computer randomization. All study personnel will remain blinded to treatment assignments until the conclusion of the entire study, with the exception of the pharmacist and the statistician. These individuals will not disclose any information regarding the treatment assignment of individual subjects to the study investigators.

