13. DATA ANALYSIS AND MONITORING

13.1. Sample Size Determination

The currently planned enrollment target of 40 subjects (*i.e.* 20 subjects per arm) is intended to achieve a final sample size of 30 and assumes a dropout rate of 25% during the course of the study. In turn, this estimate is based on the number of acute ischemic stroke patients who presented to Strong Memorial Hospital with an isolated visual field deficit in the previous calendar year (56 patients between January 1, 2015 and December 31, 2015). Previous studies indicate that 50% of patients will experience an improvement in their visual field deficit by 3 months. Based on this rate of spontaneous recovery, a final sample size of 15 subjects per group will provide 80% power to detect an improvement rate of 90% in the actively treated group (*i.e.* a 40% difference between the fluoxetine and placebo groups), using a one-sided χ^2 test with $\alpha = 0.05$. Thus, the planned sample size will be sufficient to detect a moderately large effect and is comparable to sample sizes used in equivalent pilot trials evaluating the efficacy of an FDA-approved drug for a novel application.

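### The primary endpoint is worded as an unjustified yes/no cut at 15 degrees while the rationale and named test point to the amount of gain; if the cut is what is analysed, power is probably, but not certainly, lost

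*Combined protocol and SAP*

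**What the plan says.** Section 13.2 defines the outcome by a threshold: "The primary endpoint will be an improvement in peripheral vision of at least 15 degrees in the affected visual field", on automated Humphrey perimetry at 6 months. It then names the comparison: "The primary outcome will be compared between the treatment groups using an upper-tailed two-sample *t* test with $\alpha = 0.05".

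Section 13.1 sizes the trial on rates. The control rate comes from this sentence: "Previous studies indicate that 50% of patients will experience an improvement in their visual field deficit by 3 months". The claim is that "a final sample size of 15 subjects per group will provide 80% power to detect an improvement rate of 90% in the actively treated group", "using a one-sided χ^2 test with $\alpha = 0.05".

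Section 2.2 describes the intended comparison in graded terms: "The degree of improvement in visual function will then be directly compared between the treatment group and the control group".

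Section 5.2 (item 3) describes the 24-2 perimetry test but does not say how degrees of gain are to be derived from it. No section gives a clinical, regulatory or measurement reason for choosing 15 degrees. No section gives an SD or a distribution for the gain.

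**The concern.** Perimetry yields a graded result. A yes/no cut at 15 degrees treats a gain of 14 degrees as no gain, and a gain of 15 as equal to full recovery. With 30 completers the trial has little information to spare, and its stated 80% power applies only to the large contrast of 50% versus 90%.

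The plan does not settle which variable enters the primary analysis. The endpoint wording and the sizing point to yes/no. The rationale and the t test point to degrees. If the inconsistency is later resolved towards yes/no, the within-category information is given up by default, without a stated reason. The amount of gain comes from the same perimetry, already scheduled at baseline and 6 months.

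**Working it through.** **Inputs.** From Section 13.1: 15 per arm, 50% versus 90%, one-sided alpha 0.05, chi-square. From Section 8.3: 1:1 allocation. Assumed, because the documents are silent: the 50% and 90% are the shares above the 15-degree cut at 6 months, and the gain follows the distribution named at each step.

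**1. The plan's own figure.** Power = Φ{[Δ − 1.645·SE0] / SE1}, with SE0 = √(2·p̄(1−p̄)/n) and SE1 = √([p1(1−p1) + p2(1−p2)]/n).
- p̄ = 0.70, SE0 = √(2·0.70·0.30/15) = 0.167, SE1 = √((0.25 + 0.09)/15) = 0.151.
- (0.40 − 1.645·0.167)/0.151 = 0.83, so power is 79.6%. The stated 80% reproduces.
- Exact enumeration of the uncorrected chi-square gives 83.4%. A t test applied to 0/1 values gives 79.3%.

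**2. Graded gain, assumed normal with equal SD.** If half of controls and 90% of treated patients exceed the cut, the shift is z(0.90) − z(0.50) = 1.28 SD. Noncentrality = 1.28·√(15/2) = 3.51 on 28 df, so one-sided power is 96.2%. The difference from yes/no is 96.2 − 83.4 = 12.8 points (exact) or 96.2 − 79.6 = 16.6 points (formula).

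**3. Smaller effect, 50% versus 80%.** Yes/no: (0.30 − 1.645·0.174)/0.165 = 0.08, power 53% (exact 56%). Graded: shift 0.84 SD, noncentrality 2.30, power 73%.

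**4. Detectable difference.** On the graded scale, 80% power needs about 0.93 SD, which equals 82% versus 50% above a cut at the control median.

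**5. Moving the cut.** Keep the 1.28 SD shift but suppose only 20% to 30% of controls exceed 15 degrees. Yes/no power is then about 86% to 87%, and the loss about 10 points.

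**6. Other distributions, 50% versus 90% above the cut.** Figures are simulated, with at least 8,000 runs behind those checked, so the standard error is at most √(0.25/8000) = 0.6 point. Compare each with 79.6% to 83.4% for yes/no.

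| Assumed gain | t test | Rank test |
|---|---|---|
| Normal shift | 96% | 95% |
| Logistic shift | 94% | 95% |
| Floor and ceiling (values limited to 0–24, SD 10 or 20) | about 90–94% | about 90–94% |
| Log-normal, log-SD 0.8 / 1.0 / 1.5 | 91% / 87% / 72% | about 95–96% |
| Non-improvers near 0 (SD 1 to 5), improvers even over 15–40 degrees | about 72% | about 60% |
| Improvers gain 20 degrees more than non-improvers, noise SD 1 to 5 | 81% to 71% | about 60% |

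The graded analysis wins in the first three rows. In the fourth, the rank test wins throughout, but the t test falls below yes/no at the heaviest skew. In the last two, graded analysis gives no clear gain or loses.

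**The case against.** The strongest reply is that the loss may not exist. The plan names a t test, and Section 2.2 speaks of degree, so the sponsor may already intend to compare degrees gained. That stands: the documents do not settle it, and the point has to be conditional on a yes/no analysis.

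A reader might also infer that the plan forfeits 13 to 17 points of power. The documents do not support that as a finding. The range reflects only which power method is used for the binary test; the distribution of gain matters more and is not given. The anchor is borrowed too: the 50% is any improvement by 3 months, not a gain of at least 15 degrees at 6 months.

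The adverse case is not far-fetched. Section 13.1 speaks of half of patients improving, which is at least as compatible with improvers and non-improvers as with a smooth shift. On the other side, Section 1.2 describes a gradual, partial return of function, which fits a graded outcome better than an all-or-none one. Neither passage decides the matter.

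Nor does the cut ignore partial recovery as such. A gain of 15 degrees can itself be partial, so only gains below the cut go uncounted.

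Finally, the graded outcome needs care. Section 3.2 admits both hemianopia and quadrantanopia, so the room to improve may differ between patients and strain the equal-SD assumption.

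**Conclusion.** The point holds in conditional form. The 15-degree cut is unjustified, and the plan does not say whether yes/no results or degrees enter the primary test. If yes/no is analysed, then under an assumed normal, equal-SD shift power at 15 per arm is about 80% to 83% rather than about 96% at 50% versus 90%, and 53% to 56% rather than 73% at 50% versus 80%. The advantage persists with floor and ceiling effects. With skewed gain it depends on the test chosen, and it disappears or reverses if recovery is nearly all-or-none. This is a worthwhile, low-cost improvement that agrees with the plan's own rationale and named test. It is not proof that the planned analysis is underpowered.

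**What to change.** - **Section 13.2.** Make the primary outcome the baseline-to-6-month change in the affected field on Humphrey perimetry, kept graded and in one pre-specified metric with its unit and derivation. Compare arms with the t test already named, and pre-specify a Wilcoxon rank-sum test as the supporting analysis. Keep the proportion gaining at least 15 degrees as a key secondary outcome, with a reason for the cut.
- **Section 13.1.** Restate power on that outcome: 15 per arm gives 80% power for a difference of about 0.93 SD, one-sided alpha 0.05.
- **Timing.** Make the change before anyone sees outcome data by arm. This includes the statistician, whom Section 8.3 exempts from blinding.

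The cost is wording only: no added patients, visits or tests. There are two downsides. A mean difference is less direct to interpret than a responder rate, and the power gain vanishes or reverses if recovery is close to all-or-none.

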3.2. Inclusion and Exclusion Criteria

- a) **Inclusion Criteria:** Patients between 18 and 85 years of age who are admitted to Strong Memorial Hospital with an MRI-confirmed acute ischemic stroke resulting in a clinically verifiable isolated right-sided or left-sided homonymous hemianopia or quadrantanopia will be eligible for inclusion in the study.
- b) **Exclusion Criteria:**
 - Known hypersensitivity reaction to fluoxetine or other SSRIs
 - National Institutes of Health Stroke Scale (NIHSS) score greater than 5
 - Premorbid modified Rankin Scale (mRS) score greater than 2
 - Premorbid monocular or binocular visual field deficits
 - Premorbid retinopathy or optic neuropathy
 - Premorbid depression
 - History of cognitive impairment, dementia, or neurodegenerative disorder
 - History of seizure disorder
 - History of mania or hypomania
 - History of hyponatremia
 - History of angle-closure glaucoma or elevated intraocular pressure
 - Current alcohol abuse or impaired liver function
 - Current use of an antidepressant medication
 - Current use of a medication likely to have an adverse interaction with fluoxetine
 - Current use of a medication likely to impair post-stroke recovery
 - Contraindication to MRI
 - Pregnancy or lactation
 - Hemorrhagic transformation of the index stroke, resulting in mass effect
 - Enrollment in another clinical trial at the time of the index stroke

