5. METHODS AND STUDY PROCEDURES

Subjects will be evaluated at five time points as indicated in the Table: at baseline (*i.e.* during the acute hospitalization immediately after enrollment in the study) and at 7 days, 30 days, 90 days, and 6 months after randomization. They will be contacted by phone 7 days after the initiation of the study drug to screen for any adverse events using an adverse event questionnaire (Appendix H). This questionnaire will be administered in the hospital if the patient has not been discharged yet, and repeated at the remaining time points.

At baseline, the premorbid mRS, Patient Health Questionnaire-9 (PHQ-9), and Visual Function Questionnaire-25 (VFQ-25) scores will be determined for each subject. As part of standard care, subjects will undergo a formal neuro-ophthalmological examination to confirm and characterize their visual field deficits. This will also help to rule out ocular, motor, or cognitive deficits likely to impair their ability to perform the visual function tests required by the study protocol. In addition, subjects will be evaluated by ocular coherence tomography to determine baseline RNFL thickness, neuropsychological testing to assess their ability to perform certain visual tasks, and fMRI for retinotopic mapping of the early visual cortex. To ensure that potential subjects do not have any hematologic abnormalities (*e.g.* thrombocytopenia) or metabolic derangements (*e.g.* hyponatremia, hepatic insufficiency) that may affect the safety of taking fluoxetine, all candidates will have a complete blood count (CBC) and comprehensive metabolic panel (CMP) drawn at baseline. Women of childbearing age will have a urine pregnancy test to make sure they are not pregnant. Finally, because some SSRIs like citalopram have been associated with QT interval prolongation, each patient's baseline electrocardiogram (ECG) will be assessed for possible arrhythmias prior to randomization.

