Subjects will be started on fluoxetine *vs.* placebo within 5 days of the index stroke and no later than 72 hours after their admission to the hospital. Seven days after randomization, they will be called by telephone and assessed for any adverse events using a questionnaire. If the subject has not been discharged from the hospital yet, this assessment will be performed in person in the hospital. Subjects will return for study-specific and routine evaluations at 30 days, 90 days, and 6 months following the initiation of treatment. During these visits, they will undergo assessments that constitute standard care as well as study-specific evaluations and monitoring, as indicated in the Table.

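### The primary 6-month comparison ignores baseline field loss, which is already measured; with 15 per arm this gives up precision if baseline predicts recovery

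*Combined protocol and SAP*

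**What the plan says.** Section 13.2 defines the primary endpoint as "an improvement in peripheral vision of at least 15 degrees in the affected visual field", measured by automated Humphrey perimetry at 6 months. It then gives the whole primary analysis in one sentence: "The primary outcome will be compared between the treatment groups using an upper-tailed two-sample" *t* test with α = 0.05. No covariate is named there or elsewhere.

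Section 13.1 sizes the trial on response rates: "a final sample size of 15 subjects per group will provide 80% power to detect an improvement rate of 90" percent under active treatment, against 50% spontaneous improvement, using a one-sided χ² test at 0.05.

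Section 8.3 says only this about allocation: "Subjects will be randomized in a ratio of 1:1 to fluoxetine vs. placebo by computer randomization". It names no stratification factor.

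Baseline field information is already collected. Section 5.2 (item 3) and the schedule Table place SITA standard 24-2 perimetry at baseline as standard care. Section 3.2 admits patients with "isolated right-sided or left-sided homonymous hemianopia or quadrantanopia", and Section 5 adds that "subjects will undergo a formal neuro-ophthalmological examination to confirm and characterize their visual field deficits".

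On timing, Section 5 places the baseline assessment "during the acute hospitalization immediately after enrollment in the study" and starts study drug "within 5 days of the index stroke and no later than 72 hours after their admission to the hospital". It does not say that perimetry comes before the first dose.

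**The concern.** Eligible patients start with fields of different size. A gain of a fixed number of degrees plausibly depends on how much field was lost, since a smaller deficit leaves less room to gain 15 degrees. If so, part of the outcome variation between patients is predictable at entry, and an unadjusted test leaves it in the error term.

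Baseline does enter the endpoint, because improvement is counted from it. That is not adjustment: a change or responder score can still depend on the starting value.

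The design has little slack. With about 15 patients per arm, 80% power requires a 40-point difference; if the true treated rate were 80% instead of 90%, the unadjusted power would be 52%. Chance imbalance is also common at this size. The probability of a difference of at least 0.5 SD in mean baseline field loss is 2[1 − Φ(0.5√7.5)] = 17%. A decision to adjust made after seeing such an imbalance would look data-driven, so the choice belongs in the plan.

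**Working it through.** **Inputs from the documents:** 15 per arm, 50% vs 90%, one-sided α = 0.05 (13.1); two-sample *t* test (13.2). **Not in the documents:** any SD, any correlation between baseline and outcome, and the mix of deficit types. These are assumed over ranges.

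**Step 1. Reproduce the stated power.** Pooled one-sided formula, mean rate 0.70:

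power = Φ{[0.40 − 1.645·√(2·0.70·0.30/15)] / √(0.50·0.50/15 + 0.90·0.10/15)} = Φ{(0.400 − 0.275)/0.1506} = Φ(0.83) = 79.6%.

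The stated 80% holds without covariates. The *t* test applied to the 0/1 outcome, by exact enumeration, has power 79.3% and level 4.2% to 5.0% for null rates of 30% to 90%.

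**Step 2. Responder endpoint, adjusted.** Each patient has a normally distributed latent recovery with correlation ρ to baseline field loss, cut so that the arm rates are 50% and 90%. The 0/1 outcome is fitted by a linear model with the model-based standard error. The two-covariate column adds a hemianopia/quadrantanopia indicator whose underlying scale correlates 0.6 with baseline and which has no separate effect. There were 60,000 simulated trials per row.

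| ρ (assumed) | Unadjusted | Baseline only | Baseline + deficit type |
|---|---|---|---|
| 0 | 79.3% | 79.8% | 78.6% |
| 0.3 | 79.3% | 81.3% | 79.9% |
| 0.5 | 79.3% | 84.8% | 83.5% |
| 0.7 | 79.3% | 89.4% | 88.3% |

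A separate baseline-only simulation of the same model (40,000 trials per setting) gave 79.6%, 81.2%, 84.7% and 89.3%. Its level was 4.1% to 5.2% across null rates of 30%, 50%, 70% and 90%.

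**Step 3. Continuous outcome, adjusted.** Set the effect so that a change-score *t* test has 80% power: d = 0.931 SD of change, 28 df. With equal variances at the two times and baseline-to-6-month correlation r, the change score has variance 2(1 − r)σ² and the ANCOVA residual has (1 − r²)σ². The ratio is (1 + r)/2. Estimating one covariate inflates the variance by about 27/26. The noncentrality is therefore 0.931·√7.5 / √[(1 + r)/2 · 27/26], on 27 df.

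| r (assumed) | (1 + r)/2 | Formula | Simulated, baseline only | Simulated, baseline + deficit type |
|---|---|---|---|---|
| 0.3 | 0.65 | 91.6% | 91.3% | 90.4% |
| 0.5 | 0.75 | 87.9% | 88.1% | 86.9% |
| 0.7 | 0.85 | 84.1% | 84.2% | 82.9% |
| 0.9 | 0.95 | 80.4% | 80.0% | 78.7% |

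The change score is 80% throughout. The variances break even at r = 2·26/27 − 1 = 0.93. In the limit where baseline says nothing about the change (ratio 1), the formula gives 78.6%, a loss of about 1.4 points.

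**Step 4. Is deficit type worth adding?** In both tables it lowers power by about 1 point in every row. It helps only if given a separate effect: with assumed placebo response of 35% and 65% by type in a 50:50 mix, adjusting for type alone gives 82%. Under the model of Step 2, type alone gives 79.5%, 80.0%, 80.7% and 81.7%, a gain of 0 to 2 points.

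**Step 5. Why not logistic regression.** At a 90% rate, the chance that all 15 treated patients respond is 0.9¹⁵ = 20.6%, and then no finite arm estimate exists.

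**The case against.** The strongest reply is that nothing here is an error. The unadjusted test is valid under randomization, the stated power reproduces, and the protocol likens its sample size to that of pilot trials. No passage says that baseline field loss predicts recovery. On the responder endpoint the gain is about 2 points at a correlation of 0.3, and the 89% figure needs 0.7. All of this stands. It limits the point to a conditional, inexpensive improvement.

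A second reply is that no covariate model can be fixed until the outcome scale is. Section 13.1 tests a rate with χ², while 13.2 applies a *t* test to a threshold endpoint. That also stands, so the fix gives one model for each scale.

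A third concerns the standard error. The results above assume 15 vs 15. If dropout left 18 treated and 12 placebo patients at 90% and 50%, the model-based 95% interval, checked for the model with both covariates, would cover about 92%. The unadjusted pooled interval does no better, at about 91%. This is a caveat on reporting and gives no reason to leave baseline out.

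A reader might infer that deficit type must also be adjusted for, or randomization stratified by it, because both types are eligible and a gap of three or more patients between arms has a 36% chance at a 50:50 mix. The documents do not support that. They give no reason to expect deficit type to predict recovery beyond the extent of field loss, and without such an effect it costs power.

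**Conclusion.** The point holds as a matter of precision. Section 13.2 leaves an already collected baseline measure out of the primary comparison. If that measure predicts recovery, power is given up: about 2 points at an assumed correlation of 0.3, 5 to 6 at 0.5 and 10 at 0.7 on the responder endpoint. On a continuous outcome the gain over a change-score test runs from about 11 points at r = 0.3 to none at r = 0.9. These figures rest on 15 completers per arm, equal arms, a normal latent model (responder) or equal variances (continuous), and correlations that the documents do not supply.

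A reader might infer that the planned test is biased or the power statement wrong. Neither follows: the level is kept and the 80% reproduces. Nor would adjustment rescue an optimistic effect. With a true treated rate of 80%, even the two-covariate model at ρ = 0.7 reaches only 64%.

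It is worth doing because it must be settled before unblinding and costs almost nothing. Confidence in the size of the gain is moderate at best.

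**What to change.** First settle in 13.2 whether the primary outcome is the 15-degree responder status or a continuous field measure. Then pre-specify baseline perimetric field loss as the single covariate, taken from the same 24-2 measure that defines the endpoint and recorded before the first dose.

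- **Responder endpoint kept:** a linear model of the 0/1 outcome on arm and baseline field loss, one-sided 0.05, reporting the adjusted risk difference. Do not use ordinary logistic regression.
- **Continuous outcome:** ANCOVA of the 6-month value on arm and baseline.

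Add deficit type only if Section 8.3 is changed to stratify by it, or if the investigators state why it should predict recovery beyond baseline field loss. Say in Section 5 that baseline perimetry precedes the first dose. If pre-dose perimetry proves unavailable and deficit type is to replace it as covariate, decide that once, for the whole trial, before unblinding.

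The cost is a few sentences and one degree of freedom. No visit, test or patient is added, and with the responder endpoint kept the 50% vs 90% rationale is unchanged. If baseline proves unrelated to recovery, there is little or no power loss on the responder endpoint and about 1.4 points on a continuous one.
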